- ✓ Study treatment period: The imaging examination cycles will start from C1D1. In the first 16 treatment cycles, imaging examinations will be performed once every 2 cycles (the first assessment will be on C3D1), and once every 4 cycles thereafter. If radiographic progression is noted and pseudoprogression has been ruled out, imaging examinations will no longer be performed; subjects who discontinue the study treatment for reasons other than radiographic progression will still be followed up according to the established cycle. If the previous imaging examination does not show progression and no imaging examination is performed within 4 weeks before the 30-day visit after the last dose, an imaging examination must be performed at the 30-day visit after the last dose. The time window for tumor evaluation is \pm 7 days. Additional tumor evaluations may be performed if PD is suspected (for example, worsening of symptoms).

[18] Dispensation/retrieval of drugs and study treatment: SHR-1210 200 mg, intravenous drip infusion, once every 3 weeks starting from C1D1; if SHR-1210 administration of the current cycle cannot be performed due to adverse events, it can be delayed for up to 7 days from the scheduled administration point. SHR-1210 will not be administered in this cycle if the scheduled administration is delayed for more than 7 days. Apatinib 500 mg, continuous oral administration, once daily. Each treatment cycle lasts for 21 days. The first dose of apatinib will be dispensed on C1D1 or one day in advance; subsequent apatinib tablets are allowed to be dispensed at the scheduled time point within \pm 3 days; remaining apatinib must be retrieved before each dispensation. For dose interruption due to AEs or other reasons, unscheduled drug dispensation and retrieval are permitted.

[19] Adverse events: Recorded from the date of signing the informed consent form to the end of the safety follow-up period or the start of a new anti-tumor treatment. See [Table 11. Principles of AE/SAE collection and follow-up](#) for details.

[20] Concomitant medication/treatment: Recorded from 28 days before the first dose of study treatment to the end of the safety follow-up period; If a new anti-tumor treatment is started during this period, only concomitant medications for treatment-related adverse events will be recorded thereafter. After the safety follow-up period, only concomitant medications/treatments for adverse events are required to be recorded.

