- [17] Tumor imaging evaluation: CT or MRI of lesions in the head, chest, abdomen, pelvis, and other sites. Sites with bone metastasis as shown by bone scans, PET-CT, or clinical indications must also be reexamined by CT or MRI at baseline but no longer undergo bone scan or PET-CT for efficacy follow-up. CT or MRI follow-ups of lesions in the head, chest, abdomen, pelvis, and other sites will be performed at each response evaluation. The CT/MRI examination methods and techniques for a subject shall remain the same throughout the study period.
 - ✓ At screening, tumor evaluations (at this study center only) up to 4 weeks before the first dose and before signing the informed consent may be used as long as they meet the requirements.

- ✓ Study treatment period: The imaging examination cycles will start from C1D1. In the first 16 treatment cycles, imaging examinations will be performed once every 2 cycles (the first assessment will be on C3D1), and once every 4 cycles thereafter. Imaging examinations will no longer be performed in case of radiographic progression; subjects who discontinue the study treatment for reasons other than radiographic progression will still be followed up according to the established cycle. If the previous imaging examination does not show progression and no imaging examination is performed within 4 weeks before the 21-day visit after the last dose, an imaging examination must be performed at the 21-day visit after the last dose. The time window for tumor evaluation is \pm 7 days. Additional tumor evaluations may be performed if PD is suspected (for example, worsening of symptoms).
- [18] Study treatment: (doxorubicin + ifosfamide/ifosfamide monotherapy): doxorubicin 60 mg/m², on D1, ifosfamide 2 g/m²/d, on D1-D4, q3w, and 6 cycles are recommended; if the investigator considers that the subject benefits from the chemotherapy, additional chemotherapy cycles may be administered; the content of visits in subsequent treatment cycles will be the same as those in cycles 2-6. If intolerance is noted, the investigator may delay the administration of this cycle or the chemotherapy drug, and adjust the administration time of the next cycle to 21 days after the administration of the previous cycle. If the maximum cumulative dose of doxorubicin is reached, the treatment will be switched to ifosfamide monotherapy 2 g/m²/d on D1-D5 q3w.

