◆ **The following should be completed on day 1 of every 2 cycles from cycle 3 onwards:**

- Urinalysis
- Coagulation function
- Thyroid function
- Blood pregnancy test
- Tumor imaging examination: Imaging examinations will be performed once every 2 cycles (6 weeks) in the first 16 treatment cycles of the study treatment period and once every 4 cycles (12 weeks) thereafter. Imaging conditions should be the same as those at baseline (including slice thickness and contrast agent). The time window for imaging examination is \pm 7 days. Additional imaging evaluations may be performed if PD is suspected (e.g., worsening of symptoms)
- Quality of life score

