4.1.2.5 Best overall response (BOR)

The best overall response (BOR) is calculated based on the evaluation of imaging efficacy of soft tissue of all visits. The best response until the last response evaluation shall be used if no progressive disease is noted during the period between the date of first dose and the date of PD or initiation of other anti-tumor treatments. BOR is classified as: CR, PR, SD, PD, and NE. If the tumor is assessed as PD at a visit, the date of the PD should be recorded as the date of imaging assessment of the target lesion, the date of imaging assessment of the non-target lesion, or the date of discovery of the new lesion, whichever is earlier.

- Confirmed CR: Response evaluation of CR that has been reconfirmed as CR in a response evaluation 4 weeks later.
- Confirmed PR:
 - Response evaluation as CR that has been reconfirmed as PR instead of CR.
 - Response evaluation as PR that has been reconfirmed as CR/PR in a response evaluation 4 weeks later.
- SD:
 - Response evaluation as CR/PR that has been reconfirmed as SD instead of CR/PR.
 - The response is evaluated as SD at least once within the shortest time interval (not less than 6 weeks) after the start of the study.

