5.1.2 General rules and analysis

Baseline

Unless otherwise stated, "baseline" in this study is defined as the last non-missing measurement value obtained before the first use of study drugs.

Study days

The day of the first dose is used as the start date of the study (Day 1).

- If the evaluation date (adverse event, laboratory tests, etc.) is on or after the study medication, the study date shall be calculated as follows:

Study days = evaluation/event date – start date of study + 1.

- If the evaluation date (baseline characteristics, medical history, etc.) is before the study medication, the number of study days is a negative figure and shall be calculated as follows:

Study days = evaluation/event date – start date of study;

General analysis

Unless otherwise specified, the following descriptive statistics will be summarized by the type of variables:

- The measurement data will be summarized using mean, standard deviation, median, maximum, minimum, and quartile.
- Count data will be summarized using frequency and percentage;
- For time-to-event data, Kaplan-Meier method will be used to estimate the survival function and median time to event onset, and a survival curve will be plotted.

Number of decimal places

Unless otherwise specified, number of decimal places in the analysis report will be determined as per the following rules:

- The decimal places of the minimum and maximum will remain the same as that of raw data to be acquired; there should be one additional decimal place for the mean and median, and 2 additional decimal places for standard deviation, up to 4 decimal places.
- The percentage will be rounded to 1 decimal place. If the frequency is 0, the percentage is not displayed.
- The *P* value will retain 4 decimal places. If the *P* value is < 0.0001, it will be expressed as "< 0.0001"; if the *P* value is > 0.9999, it will be reported as "> 0.9999".
- The 95% CI, if being a decimal, will retain at least 2 decimal places, up to 4 decimal places. Details are as follows: The 95% confidence interval will have one more decimal place than that of the raw data. If the raw data have no decimal place, the 95% confidence interval will retain 2 decimal places; if the raw data have 4 or more decimal places, the 95% confidence interval will retain at most 4 decimal places.
- Time to event (in months) will be rounded to one decimal place.

Results of Laboratory Tests

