^a: If a CR is truly met at first time point, then efficacy of any disease seen at a subsequent time point, even disease meeting PR criteria relative to baseline, will still be evaluated as PD at that point (since disease will reappear after CR). Best response will depend on whether minimum duration for SD is met. However, sometimes CR may be claimed when subsequent scans suggest small lesions are likely still present and in fact the subject has PR, not CR at the first time point. Under these circumstances, the original CR should be changed to PR and the best response is PR.

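### The 6-week minimum for stable disease makes no allowance for the ±7-day scan window, so a compliant first scan on days 35 to 41 cannot establish SD

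*SAP*

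**What the plan says.** **Minimum for SD.** SAP 4.1.2.5 grants a BOR of SD when the response is "evaluated as SD at least once within the shortest time interval (not less than 6 weeks) after the start of the study". It mentions no visit window. SAP 5.1.2 supplies the clock: "The day of the first dose is used as the start date of the study (Day 1").

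**Scan timing.** In both arms the protocol's flow diagrams (sections 1 and 2, footnote [17]) schedule imaging in the first 16 cycles "once every 2 cycles (the first assessment will be on C3D1), and once every 4 cycles thereafter". Cycles last 21 days, and protocol 11.2.1 equates the interval with weeks: "Imaging examinations will be performed once every 2 cycles (6 weeks) in the first 16 treatment cycles". On tolerance, footnote [17] says "The time window for tumor evaluation is" ± 7 days.

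**Consequence of an early SD.** Under SAP Appendix 1, 4.4.3, an SD that misses the minimum does not settle BOR, and later assessments decide. Its worked examples make SD then PD a BOR of PD, and SD then loss to follow-up not evaluable. DCR (SAP 4.1.2.3) counts treated subjects whose BOR is CR, PR or SD.

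**CR then PR.** SAP 4.1.2.5 lists under confirmed PR, without condition: "Response evaluation as CR that has been reconfirmed as PR instead of CR". Table 3 of SAP Appendix 1 gives three possible outcomes for that sequence (SD, PD or PR). Footnote a explains that after a true CR, disease seen later "will still be evaluated as PD at that point (since disease will reappear after CR"), with BOR then depending on the SD minimum. BOR is PR only if the first CR was really a PR.

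**The concern.** The nominal first scan sits exactly on the SD threshold, and the protocol allows it to be up to a week earlier. Two subjects with the same disease course, stable at the first scan and progressed at the second, can therefore be classed differently because one was scanned on day 40 and the other on day 43. Neither site deviated from protocol.

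DCR is a secondary endpoint, assessed by both the investigator and the IRC, and reported with a between-group difference and 95% CI (SAP 5.4.2). A classification that turns on the booking day lowers DCR relative to a window-adjusted rule. It could also disturb the comparison if early scans are more common in one arm.

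The CR-then-PR line raises a smaller issue of the same kind: the SAP body is less specific than its own appendix, so a programmer has two rules to choose from.

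**Working it through.** **Step 1: the plan's own figure.** First scan = 2 cycles × 21 days = 42 days after first dose = 6.0 weeks. This agrees with the protocol.

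**Step 2: window against minimum.**
- Permitted days: 42 − 7 = 35 to 42 + 7 = 49, which is 15 days.
- Days below 42: 35 to 41, which is 7 days. 7/15 = 47%.
- C3D1 is study day 43. If 6 weeks is read as study day 42, then 6 of 15 days fail (40%).
- With a 35-day minimum, 0 of 15 fail.
- The second scan is due at 84 days, earliest 84 − 7 = 77, so SD there always qualifies.

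**Step 3: who is affected.** Take a subject with SD on a day 35–41 scan:

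| Next evaluable result | BOR as written | In DCR numerator? |
|---|---|---|
| SD, or a response later confirmed | SD or response | Yes, no change |
| PD | PD | No |
| None | NE | No |

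Because SAP 4.1.2.5 asks for confirmation of response 4 weeks later, a PR on day 35–41 followed by PD is exposed too. Table 3 makes it SD only if the SD minimum is met, otherwise PD.

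**Step 4: illustrative size.** Inputs are the planning medians of 4.5 and 7.0 months (SAP 2.3) and 30.4375 days per month (the conversion in SAP 5.1.3). Exponential PFS is an assumption: S(t) = exp(−ln 2 × t / median). Six weeks = 42/30.4375 = 1.380 months; twelve weeks = 2.760 months.
- Control: S(6 wk) − S(12 wk) = 0.8085 − 0.6537 = 0.1548
- Investigational: 0.8723 − 0.7609 = 0.1114

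Let f be the share of first scans done on days 35–41. The documents do not give it, so a range is shown. Loss in DCR points through SD then PD:

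| f (same in both arms) | Control, 15.48f | Investigational, 11.14f | Gap |
|---|---|---|---|
| 0 | 0 | 0 | 0 |
| 10% | 1.5 | 1.1 | 0.4 |
| 20% | 3.1 | 2.2 | 0.9 |
| 47% (scan days even over the window) | 7.2 | 5.2 | 2.0 |

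These are approximations, not bounds. The interval used is weeks 6 to 12, while the affected scans fall slightly earlier. Subjects with no later scan would add to the loss.

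**Step 5: direction between arms.** With equal f, control loses more. But f need not be equal. At 10% in control and 20% in the investigational arm, the losses are 1.5 and 2.2 points and the order reverses. The break-even ratio of investigational f to control f is 15.48/11.14 = 1.39.

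**Step 6: CR then PR, side by side.** SAP 4.1.2.5 always gives PR. Table 3 with footnote a gives PR if the first CR is re-read as PR; otherwise PD at the second scan, with BOR of SD or PD according to the SD minimum. The two agree in the first case and differ in the second.

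**The case against.** **The 6-week minimum is standard.** SAP Appendix 1, 4.6.1 speaks of 6 to 8 weeks in general, so 42 days is already at the short end and 35 lies below it. Strict application could be a deliberate, conservative choice. It is true that the minimum itself is not at fault. But nothing in the SAP shows that the sponsor meant to exclude compliant scans, and the nominal visit lies on the threshold itself.

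**The clock may start elsewhere.** SAP Appendix 1, 4.6.3 measures stable disease from randomization in randomized trials. The flow diagrams place randomization between day −7 and C1D1. With a lag of k days to first dose, only 7 − k days fail, and none at k = 7. SAP 5.1.2 favours first dose, but 4.1.2.5 names no origin. This stands as a reason to name one.

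**The size may be trivial.** Scans are anchored to C3D1, and nothing supports an even spread over the window. At f = 0 the loss is nil. This stands. A reader might take the 7-point figure as the expected understatement of DCR, but it is one assumed scenario.

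**A reader might infer bias toward one arm.** Control cycles can be delayed (protocol section 2, footnote [18]; 10.1.6.4), which could push control scans later and reduce early ones. The equal-f arithmetic points the other way. The documents do not resolve this.

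**A reader might say the CR-then-PR rule contradicts Table 3 and inflates ORR.** The documents do not support that. Table 3 allows PR, and the SAP's wording can be read as describing a CR that was really a PR. The appendix is marked as for reference only and says randomized trials need no response confirmation. If unconfirmed responses count, such a subject is already a responder through the CR. ORR could rise only where confirmation governs, as 4.1.2.5 implies, and the first CR was genuine. What remains is a dropped condition.

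**Conclusion.** The mismatch is real: 7 of the 15 permitted first-scan days fail the SD minimum when the clock starts at first dose. It changes BOR only for subjects whose first scan is early and who have no later SD or confirmed response. It would be wrong to conclude that in-window scans are generally misclassified, since days 42 to 49 are unaffected and the second scan resolves everyone still stable.

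The DCR loss through SD then PD is roughly 15.5f points in control and 11.1f in the investigational arm, resting on exponential PFS at the planning medians and an unknown f. That runs from nil to 7.2/5.2 points over the range shown. The net effect on the between-arm difference cannot be signed.

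The CR-then-PR point is minor and concerns a rare sequence. DCR, ORR and BOR are secondary and carry no allocated alpha. The primary IRC-assessed PFS analysis, its 214 events and the 292 subjects are untouched. The SD rule should be corrected because the present text makes a reported endpoint depend on scan booking.

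**What to change.** In SAP 4.1.2.5:

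1. State the SD minimum as 6 weeks less the 7-day scan window, that is, at least 35 days, and name the clock origin (first dose, to agree with SAP 5.1.2). No in-window first scan then fails. If the sponsor prefers a strict 42 days, the SAP should say that this is intended and that compliant scans on days 35 to 41 do not count.
2. Make the CR-then-PR line refer to Table 3 footnote a: PR if the first CR is re-read as PR; otherwise PD at that scan, with BOR of SD or PD according to the SD minimum.

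The cost is two lines of SAP text and the matching derivation code, with no new data. SAP section 1 says the plan will be finalized before database lock, so both edits can be made before then and avoid a post-hoc choice.

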4.2 Safety Endpoints

The following safety data will be collected and summarized following the study protocol:

- Adverse event
- Laboratory test data
- Vital signs data
- 12-Lead ECG
- Physical examination
- Other safety endpoints

4.2.1 Adverse event

An AE refers to any untoward medical condition in a clinical study subject who receives a pharmaceutical product, and the condition does not necessarily have a causality with the treatment. AEs can include any unfavorable and unintended symptoms, signs, abnormal laboratory finding, or diseases, including the following:

- 1) Worsening of pre-existing (prior to entering clinical study) medical conditions/diseases (including worsening symptoms, signs, or laboratory abnormalities);
- 2) Any new AE: Any new adverse medical conditions (including symptoms, signs, and newly diagnosed diseases);
- 3) Clinically significant abnormal laboratory findings.

4.2.2 Laboratory tests

Hematology, urinalysis, stool occult blood, clinical chemistry, coagulation function, thyroid function (FT3, FT4, and TSH), myocardial zymography, and other laboratory data will be collected at the protocol-specified visit time points.

4.2.3 Vital signs

Vital signs including body temperature, heart rate, respiration, blood pressure, and pulse will be collected at the protocol-preset time points.

4.2.4 12-Lead ECG

Heart rate, QT, P-R interval, and other data will be collected at the protocol-preset time points.

4.2.5 Physical examination

Physical examination includes height, weight, general condition, head, neck, chest, abdomen, perineum, and extremities. These data will be collected at protocol-specified visit/time points.

4.2.6 Other safety endpoints

Electrocardiography and pregnancy test.

4.3 Immunogenicity and Drug Trough Concentration

- Anti-drug antibody and neutralizing antibody levels of SHR-1210
- Serum concentration of SHR-1210 and plasma concentration of apatinib

5 STATISTICAL ANALYSIS

5.1 General Considerations

5.1.1 Analysis sets

Full analysis set (FAS)

It includes all subjects who are randomized and have received study drugs at least once. This analysis set will be used for the efficacy analysis.

Per-protocol set (PPS)

It is a subset of the full analysis set, and subjects with major protocol deviations judged to have a significant impact on treatment efficacy will be excluded from this set. The list of subjects included into or excluded from the PPS should be reviewed and determined by the sponsor and the investigator before the database is locked.

Safety set (SS)

It includes all enrolled subjects who have received the study drugs at least once and have post-administration evaluable safety data.

PK concentration set

All enrolled subjects who have received at least one dose of the investigational drug and have post-baseline PK data.

Immunogenicity analysis set

All enrolled subjects who have received at least one dose of the investigational drug and have baseline and at least one post-baseline evaluable ADA data.

5.1.2 General rules and analysis

Baseline

Unless otherwise stated, "baseline" in this study is defined as the last non-missing measurement value obtained before the first use of study drugs.

Study days

The day of the first dose is used as the start date of the study (Day 1).

- If the evaluation date (adverse event, laboratory tests, etc.) is on or after the study medication, the study date shall be calculated as follows:

Study days = evaluation/event date – start date of study + 1.

- If the evaluation date (baseline characteristics, medical history, etc.) is before the study medication, the number of study days is a negative figure and shall be calculated as follows:

Study days = evaluation/event date – start date of study;

General analysis

Unless otherwise specified, the following descriptive statistics will be summarized by the type of variables:

- The measurement data will be summarized using mean, standard deviation, median, maximum, minimum, and quartile.
- Count data will be summarized using frequency and percentage;
- For time-to-event data, Kaplan-Meier method will be used to estimate the survival function and median time to event onset, and a survival curve will be plotted.

Number of decimal places

Unless otherwise specified, number of decimal places in the analysis report will be determined as per the following rules:

- The decimal places of the minimum and maximum will remain the same as that of raw data to be acquired; there should be one additional decimal place for the mean and median, and 2 additional decimal places for standard deviation, up to 4 decimal places.
- The percentage will be rounded to 1 decimal place. If the frequency is 0, the percentage is not displayed.
- The *P* value will retain 4 decimal places. If the *P* value is < 0.0001, it will be expressed as "< 0.0001"; if the *P* value is > 0.9999, it will be reported as "> 0.9999".
- The 95% CI, if being a decimal, will retain at least 2 decimal places, up to 4 decimal places. Details are as follows: The 95% confidence interval will have one more decimal place than that of the raw data. If the raw data have no decimal place, the 95% confidence interval will retain 2 decimal places; if the raw data have 4 or more decimal places, the 95% confidence interval will retain at most 4 decimal places.
- Time to event (in months) will be rounded to one decimal place.

Results of Laboratory Tests

The results of laboratory tests are generally continuous numerical variables or character variables. If continuous numerical variables recorded in eCRF contain special characters (such as < xx and > xx), the following rules will be applied:

- When there is a situation of < xx or \leq xx, half of the xx value will be used for analysis.
- When there is a situation of > xx or \geq xx, the value of xx will be used for analysis.

Analysis software

All statistical analyses will be conducted using SAS® 9.4 or later version.

